Grade 1 or 2	Maintain dose level	
Grade 3	Omit dose until resolved to \leq Grade 1, then \checkmark 1 dose level	
Grade 4	Permanently discontinue BYL719	
Skin and subcutaneous tissue disorders		
Consultation with a dermatologist is highly induced skin toxicity.	recommended for better assessment and management of BYL719-	
Grade 1(<10% body surface area (BSA) with active skin toxicity*)	Maintain dose level	

Dose Modifications for BYL719 (TREATMENT RELATED (BYL719)): This table only applies once patient has begun treatment on study and it is only applicable while they are receiving treatment on study		
	• Initiate topical corticosteroids 3-4 x daily, preferred compounds to use are Triamcinolone, Betamethasone as long as skin toxicity is active, during maximum 28 days	
	For patients with symptoms like burning and/or pruritus add non-sedating anti-histamine, consider adding a sedating anti-histamine at night	
	If active rash is not resolved within 28 days of appropriate treatment, consider adding low dose systemic corticosteroid (20-40 mg/d)	
Grade 2 (10-30% BSA with active skin	Maintain dose level.	
toxicity*)	• Initiate topical corticosteroids 3-4x daily, preferred compounds to use are Triamcinolone or Betamethasone as long as skin toxicity is active, during max. 28 days	
	Consider adding systemic corticosteroids 20-40mg/d	
	If rash resolves to \leq G1 within 10 days systemic corticosteroid may be discontinued	
	For patients with symptoms like burning, stinging and/or pruritus add non-sedating anti-histamine, consider adding a sedating anti-histamine at night	
Grade 3 (>30% BSA with active skin toxicity*)	Omit BYL719 dose until rash /skin toxicity is no longer active but fading (G1), consider exploratory skin biopsy for central assessment	
	• Initiate topical corticosteroids 3-4x daily, preferred compounds to use are Triamcinolone or Betamethasone for at least 28 days	
	Add systemic corticosteroids 20-40mg/d	
	If rash resolves to \leq G1 within 10 days systemic corticosteroid may be discontinued	
	- If rash/skin toxicity still active in up to 10% BSA after more than 14 days, continue oral corticosteroid for at least 48 hours upon rechallenge with BYL719; if rash and/or pruritus do not reoccur within 48 hours after re-challenge with BYL719, systemic corticosteroid may be discontinued	

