5.2 Definition of Dose Limiting Toxicities

- Grade 4 neutropenia (ANC < 500/mm³)
- ANC $<1000/\text{mm}^3$ with fever (temp > 101) or infection
- Grade 4 thrombocytopenia: Platelets <25,000/mm³
- Platelets <50,000/mm³ requiring transfusion
- Grade 3 or 4 treatment related non-hematologic toxicities excluding alopecia. Grade 3 nausea, vomiting or diarrhea will only be considered a dose limiting toxicity if it occurs for greater than 48 hours despite maximal medical support. Grade 3 electrolyte abnormalities will not be considered dose limiting toxicities if the electrolyte disorder can be corrected to grade 2 or less within 72 hours. A grade 4 electrolyte abnormality will be considered a DLT.
- Patients who receive < 67% of intended BYL719 or capecitabine secondary to treatment related toxicities will also be considered as having a DLT

During the MTD dose finding portion, patients who are removed from study for reasons other than a DLT, defined in section 5.2, will be replaced.

5.3 Management of Specific Toxicities are outlined below for all patients: most conservative assessments must be used for management and modification:

If a dose limiting toxicity occurs, BYL719 will be held until the toxicity reduces to \leq grade 1 at which point patients will be permanently dose reduced by 1 dose level. Patients may continue to receive their capecitabine and radiation as per institutional standard of care when toxicities resolve to \leq grade 2.

If treatment is held for more than 28 days, then patient should come off study.

During the MTD dose finding portion, patients who are removed from study for reasons other than a DLT, defined in section 5.2, will be replaced.

For toxicities other than dose limiting toxicities, specific dose adjustments, based on the worst preceding toxicity as graded by the NCI Clinical Toxicity Criteria ([NCI-CTCAE version 4.03]), are described below. A maximum of 1 dose reduction of BYL719 from the starting dose may be allowed.

Missed doses of BYL 719 are not made up and BYL719 will be stopped when radiation is completed.

Dose Modifications for BYL719 (TREATMENT RELATED (BYL719)): This table only applies once patient has begun treatment on study and it is only applicable while they are receiving treatment on study		
Worst toxicity (CTCAE 4.03 Grade)	Dose Modifications for BYL719	
HEMATOLOGICAL		
Neutropenia (ANC)		
Grade 3 (ANC < 1.0 - 0.5 x 10 ⁹ /L)	Omit dose until resolved to ≤ Grade 1, then:	

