Grade 4 ANC <0.5 x 10 ⁹ /L without fever) * this is also a DLT*	 If resolved in ≤ 7 days, then maintain dose level If resolved in > 7 days, then ↓ 1 dose level 	
ANC <1.0 x 10^9 /L with fever ($\geq 38.3^{\circ}$ C or a sustained temperature of \geq 38 °C for more than one hour)	(An ANC <1 with fever of >101 or infection is also considered a DLT) Hold BYL719 until resolved, then \checkmark 1 dose level	
Thrombocytopenia (PLT)		
Grade 3 (PLT < 50-25 x 10 ⁹ /L)	 Omit dose until resolved to ≤ Grade 1, then: If resolved in ≤ 7 days, then maintain dose level If resolved in > 7 days, then ↓ 1 dose level 	
Grade 4 (PLT < 25 x 10 ⁹ /L) *this is also a DLT*	Omit dose until resolved to \leq Grade 1, then \bigvee 1 dose level	
RENAL		
Serum creatinine		

Dose Modifications for BYL719 (TREATMENT RELATED (BYL719)): This table only applies once patient
has begun treatment on study and it is only applicable while they are receiving treatment on study

< 2 x ULN	Maintain dose level
2 – 3 x ULN	Omit dose until resolved to \leq grade 1, then:
	 If resolved in ≤ 7 days, then maintain dose level If resolved in > 7 days, then ↓ 1 dose level
Grade 3 (> 3.0 – 6.0 x ULN)	Permanently discontinue BYL719
Grade 4 (> 6.0 x ULN)	Permanently discontinue BYL719

HEPATIC

Bilirubin

(*for patients with Gilbert Syndrome these dose modifications apply to changes in direct bilirubin only)

Grade 1 (> ULN - 1.5 x ULN)	Maintain dose level with LFTs* monitored as per protocol
Grade 2 (> 1.5 - 3.0 x ULN) with ALT or AST \leq 3.0 x ULN	Omit dose until resolved to ≤ Grade 1, then: If resolved in ≤ 7 days, then maintain dose level If resolved in > 7 days, then ↓ 1 dose level
Grade 3 (> 3.0 - 10.0 x ULN) with ALT or AST \leq 3.0 x ULN	 Omit dose until resolved to ≤ Grade 1, then If resolved in ≤ 7 days, ↓ 1 dose level If resolved in > 7 days discontinue patient from BYL719
Grade 4 (> 10.0 x ULN)	Permanently discontinue BYL719

AST or ALT

Confounding factors and/or alternative causes for increased transaminases like concomitant medications, infection, hepato-biliary disorder, obstruction, liver metastasis, etc. should be excluded before dose interruption/reduction

Dose Modifications for BYL719 (TREATMENT RELATED (BYL719)): This table only applies once patient has begun treatment on study and it is only applicable while they are receiving treatment on study		
Grade 1 (> ULN – 3.0 x ULN)	Maintain dose level with LFTs* monitored per protocol	

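### The AST/ALT instruction puts the search for other causes ahead of any dose interruption, with no interim hold for a grade 3–4 rise

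*Combined protocol and SAP*

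**What the plan says.** The AST/ALT block of the section 5.3 table opens by listing possible confounders: concomitant medications, infection, hepato-biliary disorder, obstruction and liver metastasis. It says that these "should be excluded before dose interruption/reduction". It sets no deadline and does not say what happens to dosing meanwhile. The grade 2, 3 and 4 rows beneath it (without bilirubin above 2.0 x ULN) each call for omission of BYL719.

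Several other provisions bear on the point:

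- Section 5.2 makes "Grade 3 or 4 treatment related non-hematologic toxicities excluding alopecia" dose limiting, with some exceptions that do not concern transaminases. Section 5.3 then says "If a dose limiting toxicity occurs, BYL719 will be held until the toxicity reduces to" grade 1 or less, followed by a reduction of one level.
- The heading of section 5.3 adds that "most conservative assessments must be used for management and modification".
- The table is headed as applying to toxicity related to BYL719, and is introduced with the words "For toxicities other than dose limiting toxicities, specific dose adjustments".
- Section 11.5 gives general guidance for judging causality.
- Section 12.0 lets the physician stop treatment when that is in the patient's interest.

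**The concern.** Attribution is a legitimate step, because both the table and the DLT rule depend on relatedness. The difficulty is the order. BYL719 is taken once daily on a continuous schedule (section 4.1), so each day of work-up without a hold is one more dose. For a grade 3–4 rise, the lead-in postpones the omission that its own rows require. The DLT hold may not fill the gap, because it is worded for events that are treatment related and relatedness is what the work-up is meant to settle. Some of the listed causes, such as obstruction or liver metastasis, may not be excluded quickly. Stage IV patients may enter the expansion phase (section 3.1.2), so competing explanations are realistic.

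**Working it through.** **1. Order of work-up and hold within section 5.3**

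| Finding | Dose instruction | Order |
|---|---|---|
| AST/ALT grade 2–4 | Omit | Exclude other causes first |
| Glucose grade 2 | Maintain | Confounders excluded while on drug |
| Glucose grade 3 and 4 | Omit | Omit first, then check fasting status and confounders |
| Suspected pneumonitis, any grade | Interrupt | Immediately, with imaging to follow |
| Bilirubin, creatinine | By level | No exclude-first instruction |

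The order generally follows severity. AST/ALT grade 3–4 is the exception: the row says omit, and the lead-in places another step before it.

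**2. What could require a hold during the work-up**

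- *The AST/ALT row:* it requires omission, but the lead-in postpones it.
- *The DLT hold:* it needs a treatment-related event. Under section 11.5 an investigator may call the event related while no sufficient alternative has been found, but is not told to do so at that moment.
- *The most-conservative line:* it can be read as requiring a hold. It is general, and the specific AST/ALT text gives a different sequence.
- *Section 12.0:* it permits a stop but does not require one.

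An early hold is therefore supportable, but it is not expressly stated.

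**3. Doses involved**

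Inputs from section 4.1: 28 fractions, with BYL719 daily from the first to the last day of radiation. Assumption: weekday fractions without interruption.

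- Monday start: 25 fractions in 5 weeks (35 days), plus 3 days = 38 days. A Tuesday start also gives 38.
- The work-up time is not given; 1 to 7 days is assumed. The upper end borrows the weekly liver-test interval in the table's monitoring note, which is not itself a work-up time.
- Doses taken during the work-up if there is no hold: 1/38 = 2.6% to 7/38 = 18.4%.
- Doses left after a 7-day hold: 31/38 = 81.6%.
- Margin to the 67% exposure threshold in sections 4.1 and 5.2: 0.67 x 38 = 25.5, so 26 doses are needed. A 12-day hold leaves 26/38 = 68.4%; 13 days leaves 25/38 = 65.8%.

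**4. Editorial side point**

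The bilirubin rows "Grade 2 (> 1.5 - 3.0 x ULN) with ALT or AST" and "Grade 3 (> 3.0 - 10.0 x ULN) with ALT or AST" at or below 3.0 x ULN are satisfied when only one enzyme is below the limit. Take ALT 2, AST 6 and bilirubin 2.5 x ULN. This meets the bilirubin grade 2 row (omit, then resume) and also the combined AST/ALT-and-bilirubin row (permanent discontinuation). On a grid of 7 ALT x 7 AST x 9 bilirubin values = 441 cases, 96 meet both kinds of row. Requiring both enzymes to be at or below the limit brings this to 0 and leaves no abnormal case without a row. These counts show where the rows meet; they are not frequencies. After the change, the bilirubin grade 2–3 rows can still coincide with the AST/ALT grade 1 row ("Maintain dose level with LFTs* monitored per protocol"). There the most-conservative line gives omission.

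**The case against.** The strongest reply is that the protocol already leans toward holding. The lead-in says *should*, while the opening line of section 5.3 says that the most conservative assessment must govern. For an unexplained grade 3–4 rise, the conservative course is to treat it as related and omit the drug. Section 11.5 points the same way: timing that makes causality possible, with no sufficient alternative, counts as related. The DLT rule refers to treatment in general, so BYL719 need not be separated from capecitabine before the hold applies. The listed BYL719 DLTs and common adverse events (sections 2.0 and 9.1.5) include no hepatic event, and section 9.2.5 calls capecitabine hepatotoxicity uncommon.

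Most of this stands, and it limits the weight of the point. A reader might infer that the protocol requires dosing to continue, or leaves no route to a hold. The documents do not support that. What remains is that a site following the specific AST/ALT sentence would wait, and no other text tells it not to.

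A reader might also infer that the delay reaches the combined stopping row. It does not: the lead-in sits under the AST/ALT heading and speaks of interruption or reduction, while the combined row has its own heading and requires permanent discontinuation.

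**Conclusion.** The point holds as a gap in express wording for grade 3–4 AST/ALT rises whose cause is unsettled. It should be corrected, but it is modest in size: 1 to 7 of 38 doses per affected patient under the assumed work-up time, and probably few such patients among about 24. The estimate rests on an uninterrupted 38-day course and says nothing about harm. Confidence is medium, because the general provisions can be read to support an early hold.

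Two stronger readings are not supported. First, the case does not extend with equal force to grade 2. Grade 2 glucose is worked up on drug, although its row says to maintain the dose, and a grade 2 hold is more debatable. Second, the *ALT or AST* overlap might be taken for an unresolved safety contradiction. The most-conservative line already points to discontinuation. The phrase limiting the table to non-DLT toxicities does not reopen the question either, since some haematological rows are themselves marked as DLTs. The overlap is editorial and does not carry the point.

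**What to change.** Replace the AST/ALT lead-in with:

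> For grade 3–4 AST/ALT, omit BYL719 while alternative causes are assessed. If a cause unrelated to any study treatment (BYL719, capecitabine or radiation) is confirmed, BYL719 may resume at the same dose once AST/ALT has recovered to grade 1 or less, or to baseline; otherwise the rows below and the DLT rule apply.

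The recovery threshold prevents a restart while enzymes are still high. Naming all three treatments keeps a rise due to capecitabine under the DLT rule. At grade 2, leave a hold during work-up optional.

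As an editorial change, write *both ALT and AST* in the bilirubin grade 2 and 3 rows, and state that the combined discontinuation row takes precedence.

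The cost is one replaced instruction, two row edits and one precedence statement, with no added visits or tests. The clinical trade-off is some missed BYL719 doses in patients whose rise proves unrelated. The hold then runs to recovery, so it may outlast the work-up; up to 12 missed days keeps exposure above 67%.

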3.0 PATIENT ELIGIBILITY

3.1 Conditions for Patient Eligibility

- 3.1.1 Patients must have histologically proven adenocarcinoma of the rectum with no evidence of distant metastases.
- 3.1.2 The tumor must be clinically Stage II (T3-4 N0) or stage III (N+). Stage of the tumor may be determined by CT scan, endorectal ultrasound or MRI. (For patients receiving chemotherapy prior to protocol chemoradiation, the initial clinical stage applies. CT/MRI/PET should be performed within 2 months of study entry to exclude disease progression.) For the MTD expansion phase only: patients who are stage IV, and in whom it is planned to administer capecitabine and radiation then have a resection of their rectal cancer, are also eligible. Submit documentation to BrUOG on location of metastatic disease sites with source confirmation (scan, pathology etc) and obtain confirmation that patients would meet this criterion.
- 3.1.3 Measurable disease not required at baseline. Patient's without measurable disease may be enrolled as long as they clinically meet stage II or III criteria or for MTD expansion phase: also stage IV.
- 3.1.4 Patients must not have received pelvic radiation for rectal cancer, or prior pelvic radiation for any other malignancy that would prevent the patient from receiving the required radiation treatments for this study. (Patients may receive neoadjuvant chemotherapy prior to study chemoradiation)
- 3.1.5 Patients must not have an active concurrent invasive malignancy. Patients with prior malignancies, , are eligible if they are deemed by their physician to be at low risk for recurrence. For example, patients with squamous or basal cell carcinoma of the skin, melanoma in situ, carcinoma of the cervix, early stage breast cancer, or carcinoma in situ of the colon that have been effectively treated are eligible, even if these conditions were diagnosed within 3 years prior to registration.
- 3.1.6 Patients must be \geq 18 years of age,
- 3.1.7 ECOG performance status 0-1

3.1.8 ANC \geq 1,000/µl, platelets \geq 100,000/µl, total bilirubin \leq ULN (except for patients with Gilbert's syndrome who may only be included if total bilirubin is \leq 3xULN with direct bilirubin within normal range),

ALT \leq 2.5xULN, AST \leq 2.5xULN,

fasting plasma glucose \leq 140 mg/dL and HbA1c \leq 6.4% (both criteria have to be met),

 $HGB \ge 9.0g/dL$.

Serum creatinine < 1.5xULN and/or creatinine clearance > 50% LLN

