Grade 2 (> 3.0 - 5.0 x ULN) without total bilirubin elevation to >2xULN	Omit dose until resolved to \leq baseline value If treatment delay is \leq 7 days, restart at same dose If resolved in > 7 days, \checkmark 1 dose level	
Grade 3 (> 5.0 - 20.0 x ULN) without total bilirubin elevation to > 2.0 x ULN	Omit dose until resolved to \leq Baseline value, then If treatment delay is \leq 7 days, restart at same dose If resolved in > 7 days, ψ 1 dose level	
Grade 4 (> 20.0 x ULN) without bilirubin elevation to > 2.0 x ULN	Omit dose until resolved to ≤ Grade 1, then V 1 dose level	
AST or ALT and concurrent Bilirubin		
AST or ALT > 3.0 x ULN and total bilirubin > 2.0 x ULN	Permanently discontinue patient from BYL719	

All dose modifications should be based on the worst preceding toxicity.

^a Common Toxicity Criteria for Adverse Events (CTCAE Version 4.03)

*LFTs include albumin, ALT, AST, total bilirubin (fractionated if total bilirubin > 2.0 x ULN), alkaline phosphatase (fractionated if alkaline phosphatase is grade 2 or higher) and GGT. For patients with Gilbert Syndrome: total and direct bilirubin must be monitored, intensified monitoring applies to changes in direct bilirubin only; the monitoring includes the following LFTs: albumin, ALT, AST, total bilirubin (fractionated if total bilirubin > 2.0 x ULN), alkaline phosphatase (fractionated if alkaline phosphatase is grade 2 or higher) and GGT).

Patients with grade 0 or 1 at screening experiencing ALT/AST/bilirubin increase \geq grade 2 the liver function tests must be monitored weekly or more frequently if clinically indicated until resolved to \leq grade 1. In case of any occurrence of ALT/AST/bilirubin increase \geq grade 3 the liver function tests must be monitored weekly or more frequently if clinically indicated until resolved to \leq grade 1; hereafter the monitoring should be continued every other week or more frequently if clinically indicated until the end of treatment with study medication. Patients who discontinued study treatment should be monitored weekly, including LFTs or more frequently if clinically indicated until resolved to \leq grade 1 or stabilization (no CTCAE grade change over 4 weeks).

ENDOCRINE/METABOLIC

Fasting Plasma Glucose (FPG)

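### For Gilbert patients, the liver rows of the dose-modification table do not say whether total or direct bilirubin governs, so a patient eligible under 3.1.8 may meet half of a permanent-stop rule at entry or fit no row at all

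*Combined protocol and SAP*

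**What the plan says.** **Entry (3.1.8).** Total bilirubin must not exceed ULN, with an exception for "Gilbert's syndrome who may only be included if total bilirubin is \leq 3xULN with direct bilirubin within normal range". ALT and AST may each be up to 2.5 x ULN.

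**Bilirubin rows (5.3 table).** A note directly under the Bilirubin heading reads "for patients with Gilbert Syndrome these dose modifications apply to changes in direct bilirubin only". The grade 2 and 3 rows carry a transaminase condition, for example "Grade 2 (> 1.5 - 3.0 x ULN) with ALT or AST" at most 3.0 x ULN, and lead to a hold followed by restart, reduction or discontinuation depending on grade and time to recovery.

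**AST/ALT rows.** The grade 2 and grade 3 hold rows apply only where total bilirubin has not risen above 2 x ULN. The grade 4 row has the same limit but does not say which bilirubin is meant. None of the three mentions Gilbert syndrome.

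**Concurrent-elevation row.** It has its own heading. The trigger is "AST or ALT > 3.0 x ULN and total bilirubin > 2.0 x ULN" and the action is "Permanently discontinue patient from BYL719". It has no Gilbert wording and does not ask for a repeat test or a change from baseline.

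**Footnote on liver tests.** For Gilbert patients "total and direct bilirubin must be monitored, intensified monitoring applies to changes in direct bilirubin only".

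**Tie-break and scope.** The opening of 5.3 tells sites to use the most conservative assessment, and the table works from the worst preceding toxicity. The table is headed as covering toxicity related to BYL719.

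**The concern.** The eligibility rule accepts a raised total bilirubin in Gilbert patients, and one part of the table follows it by looking at direct bilirubin. The row with the heaviest consequence, and the rows that would otherwise allow a hold, use total bilirubin against a limit below the one used for entry. The protocol does not say whether the Gilbert note reaches those rows.

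Two things are at stake. One is the treatment of the individual patient: two sites could act differently on the same laboratory values. The other is the primary objective. Section 5.2 counts a patient who receives less than 67% of intended BYL719 because of treatment-related toxicity as having a DLT. Treatment-related ALT or AST in the grade 2 band (above 3.0 to 5.0 x ULN) is not itself a DLT, because 5.2 starts at grade 3 for non-haematologic toxicity. A permanent stop triggered in that band could become one through the 67% rule. In a cohort of three, one DLT forces expansion to six; a second in six makes the preceding dose level the MTD.

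**Working it through.** The plan attaches no error rate or sample-size figure to this point, so there is none to reproduce. The check compares the rows and then sizes the effect of noise.

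**Step 1: the rows side by side.** Take a Gilbert patient with total bilirubin 2.5 x ULN throughout and direct bilirubin normal (eligible under 3.1.8), whose ALT rises on treatment to 4 x ULN.

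| Reading of the Gilbert note | Concurrent-elevation row | AST/ALT grade 2 hold row | Result |
|---|---|---|---|
| Covers the Bilirubin rows only (literal placement) | Met: 4 > 3.0 and 2.5 > 2.0 | Not available: total bilirubin above 2 x ULN | Permanent stop |
| Also covers the concurrent row, not the AST/ALT rows | Not met: direct bilirubin normal | Not available: total bilirubin above 2 x ULN | No row fits |
| Covers all the liver rows | Not met | Available | Hold row |

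The text does not choose between these readings. Under the first, the bilirubin half of the stop is met on day 1 and direct bilirubin need never change.

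**Step 2: when a stop falls below 67%.** Twenty-eight fractions at five a week, started on a Monday, span 38 calendar days, with BYL719 daily. 0.67 x 38 = 25.46, so 26 doses are needed. Laboratory tests are weekly, within 3 days before each treatment week, and screening values may serve for day 1 (Section 6, footnote E). By the week 5 draw about 26 to 28 doses have been taken. Only the draws for weeks 2, 3 and 4 can therefore lead to a stop before dose 26: about 3 draws.

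**Step 3: noise with no drug effect, first reading.** Assumptions, none of them in the documents: readings are log-normal around a stable usual value and independent between draws and tests; one transaminase (ALT) is followed; usual total bilirubin is 2.5 x ULN; within-patient CV is 10%, 20% or 30% for both tests.

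- s = sqrt(ln(1 + CV²)), giving 0.0998, 0.1980 and 0.2936.
- For usual ALT b, P(ALT > 3.0) = 1 - Φ(ln(3/b)/s).
- P(bilirubin > 2.0) = 1 - Φ(ln(2/2.5)/s), giving 0.9874, 0.8701 and 0.7764.
- p is the product of the two; over 3 draws the probability is 1 - (1 - p)³.

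| Usual ALT | CV 10% | CV 20% | CV 30% |
|---|---|---|---|
| 1.5 x ULN | under 0.01% | 0.06% | 0.0091 x 0.7764 = 0.0071; 2.1% |
| 2.0 x ULN | 0.01% | 0.0203 x 0.8701 = 0.0177; 5% | 0.0836 x 0.7764 = 0.0649; 18% |
| 2.5 x ULN | 0.0338 x 0.9874 = 0.0334; 10% | 0.1786 x 0.8701 = 0.1554; 40% | 0.2673 x 0.7764 = 0.2075; 50% |

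The line is crossed by a factor of 3.0/2.5 = 1.2 at the entry ceiling but 3.0/1.0 = 3.0 from an ALT at ULN. Noise is therefore a corner case tied to high baseline transaminases.

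**Step 4: the transaminase condition in the bilirubin rows.** A patient of any kind with bilirubin 2.5, ALT 6 and AST 2.5 x ULN satisfies the grade 2 bilirubin row literally, because one of the two enzymes is at most 3.0 x ULN. The same values also satisfy the concurrent-elevation row.

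**The case against.** The strongest reply is that the protocol's intention is visible. The note and the footnote both direct attention to direct bilirubin in Gilbert patients. If the note reaches the concurrent row, nothing is met at entry, because 3.1.8 requires direct bilirubin to be normal. Equally, stopping on total bilirubin could be a deliberate safety choice, in keeping with the instruction to use the most conservative assessment. Both accounts are possible, which is why the text has to say which is meant. One could also take the AST/ALT rows to mean a new rise in bilirubin rather than a constitutional one, but the rows give no baseline reference.

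A reader might infer that half the stop is met at entry as a settled fact, and that laboratory noise will routinely supply the rest. The documents support neither: the first holds on one reading only, and the second needs a variability figure they do not give and a baseline ALT or AST near the ceiling. A reader might also infer that a constitutional bilirubin value will produce DLTs. That does not follow, because the table and the 67% rule both concern treatment-related toxicity, so a noise event counts only if it is wrongly attributed. The instruction to exclude other causes of raised transaminases helps, although it names interruption and reduction, not discontinuation. Section 4.1 adds that patients under 67% are inevaluable, a remark absent from 5.2, so the DLT consequence is itself not fully clear.

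The overlap in Step 4 is largely answered by the most-conservative rule, which selects one row. That rule does not help where no row fits, and under the literal reading it pushes sites towards the permanent stop.

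**Conclusion.** The conflict is real and rests on the text alone. Section 3.1.8, the Gilbert note and the rows that use total bilirubin do not fit together for a Gilbert patient entering above 2 x ULN. On the literal reading, any treatment-related ALT or AST above 3 x ULN leads to permanent discontinuation with direct bilirubin unchanged. If the note reaches the concurrent row alone, that patient has no applicable row.

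The reach is narrow. The documents give neither the frequency of Gilbert syndrome nor the number entering above 2 x ULN. Counting every Gilbert patient among the 24 would overstate it, and the 24 include expansion patients enrolled after the MTD is determined, for whom a DLT no longer moves it. The noise probabilities (0-18% at usual ALT 2.0 x ULN, 10-50% at 2.5 x ULN) depend on the assumed CV, independence, a usual bilirubin of 2.5 x ULN and 3 relevant draws. They illustrate the mechanism and do not predict a rate in this trial. The point merits correction because the affected rule is a permanent stop and may feed a DLT call in a cohort of 3 or 6.

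**What to change.** Reconcile 3.1.8, the Gilbert note and the table. In the concurrent-elevation row and in every AST/ALT row, state which bilirubin fraction applies to Gilbert patients and against which reference (ULN or the patient's own baseline), so that each set of values fits exactly one row. Name the fraction in the grade 4 AST/ALT row for all patients.

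As a minor tidy-up, reword the transaminase condition in the grade 2 and 3 bilirubin rows so that they cannot overlap the concurrent-elevation row.

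The sponsor's medical lead decides which rule stands; no threshold is proposed here. The cost is a wording change in one table. No new test is needed, since direct bilirubin is already required for Gilbert eligibility and monitoring.
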